A request for Waiver of Authorization is also requested for recruitment. During the first stage of the screening process, we will run an EHR case-finding program to generate an initial outreach list of potentially eligible individuals. This initial case finding algorithm does not itself qualify individuals for the study, but merely generates a likely pool within which further screening is merited.

This waiver allows study staff to approach (via letter, email/the EHR patient portal, and subsequent phone call) likely interested and eligible individuals and offer them the study opportunity. The study could not complete the research without access to and use of PHI because it is not practical to recruit eligible individuals without pre-identifying using medical record information and contact information. It would be too costly and would un-duly burden the KP membership to receive invitations to every study. Only the minimum amount of PHI will be accessed to identify participants who are likely to meet the study eligibility criteria.

6. Study Procedures

Recruitment

Recruitment procedures are described in the earlier Recruitment Methods section.

Randomization

Participants will be randomized 1:1:1 to three conditions, stratified by gender (male vs. female + all non-CIS gender identities), age (median split; estimated as <46yrs vs >= 47yrs), and minority status (white non-Hispanic vs. all other races/ethnicities).

Monitoring for Safety

The target condition is depression, and the most likely emergent risks (and how we will monitor for these) are:

- Worsening depression, evaluated at each assessment with the PHQ-9 depression measure.
- Intentional self-harm, including suicidal thoughts and behavior. This will be evaluated at each assessment with the Columbia Suicide Severity Rating Scale (C-SSRS).
- Emergent bipolar disorder symptoms (a possible risk of triggered symptoms from lightbox use). This will be assessed at each follow up assessment with the 5-item Altman Self-Rating Mania Scale (ASRM).

Any increased risk evident from any of these measures, or other unexpected increased in other less common safety issues (e.g., threats to harm others) will be reviewed between the interviewing staff and [name], with a review of the relevant usual health care the individual is already receiving.

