allows). Meta-analyses suggest an overall effect size for BLT of $d=0.84$. We conservatively estimate the effect size likely to be obtained in this pilot trial as lower than reported in meta-analyses because this is a real-world effectiveness population; even with Arm 3 adherence promotion BLT adherence is likely to be lower than in efficacy trials, leading to lower clinical benefit. Assuming a retained sample size of $N=81$ at the final 6-month assessment, we conducted power analysis for the HLM of the primary outcome (using SAS version 9.4) to determine the minimum detectable effect size. At a two-tailed alpha level of 0.05 and conservatively assuming an autocorrelation of 0.70, we would have 80% power to detect a Cohen's d for the time by arm effect as small as 0.39 for the contrast between active intervention arms (Arms 2 and 3) and TAU, and as small as 0.55 for contrasts between individual arms; both estimates are medium effects. This pilot study is not powered to evaluate mediation, but we will conduct mediation analyses as if this were the full-powered R01 confirmatory trial to test feasibility of the analytic methods and to provide informative estimates of potential mediators. We estimate that we will have 80% power using a 95% bias-corrected confidence interval to identify effect sizes of 0.43 or larger for the pathways between randomization status to mediator, and mediator to outcome (BLT adherence for MI pathway, and PHQ-9 for BLT pathway); and we will be able to identify direct and indirect effects of 0.19 or larger, which correspond to a small-medium effect.

Use of pilot results to estimate power for the future full trial. Regardless of the between-condition effect size that we observe in this pilot, we will heed the cautions that have been raised about using pilot study results to estimate effect for full trial power/sample calculations. We will consider between-condition effect size (ES) results highly tentative given the small pilot sample and will use it only with wide confidence intervals when employing it to estimate power for the future full pragmatic trial. For example, if we obtain an effect size of $d=0.45$, we will generate a power/sample size matrix with estimated effects of 0.35, 0.40, 0.45, 0.50—all ranging around the observed effect from this pilot, but trending to somewhat smaller and more conservative effects.

b. Sharing of Results with Subjects

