## Power analysis, sample size

The R34 pilot funding cap limits us to a feasibility sample that is insufficient for an adequately powered test of the hypothesis. Nonetheless, we provide an estimate of the statistical power obtained from this sample of 90 participants. Meta-analyses suggest an overall effect size for BLT of  $d=0.84$ [14]. We conservatively estimate the effect size likely to be obtained in this pilot trial as lower than reported in meta-analyses because this is a real-world effectiveness population; even with Arm 3 adherence promotion BLT adherence is likely to be lower than in efficacy trials, leading to lower clinical benefit. Assuming a retained sample size of  $N=81$  at the final 6-month assessment, we conducted power analysis for the HLM of the primary outcome (using SAS version 9.4) to determine the minimum detectable effect size. At a two-tailed alpha level of .05 and conservatively assuming an autocorrelation of .70, we would have 80% power to detect a Cohen's  $d$  for the time by arm effect as small as 0.39 for the contrast between active intervention arms (Arms 2 and 3) and TAU, and as small as 0.55 for contrasts between individual arms; both estimates are medium effects.

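### A correlation of 0.70 is called conservative without support, although a higher correlation favours the powered slope effect; the pooled detectable effect of 0.39 does not follow from the plan's own inputs (about 0.49)

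*Protocol*

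**What the plan says.** The power paragraph is in Protocol section 6.a (Power analysis, sample size) and is repeated in the SAP section of the same name. It assumes 81 participants retained "at the final 6-month assessment, we conducted power analysis for the HLM of the primary outcome". The Protocol's test is set "At a two-tailed alpha level of 0.05 and conservatively assuming an autocorrelation of 0.70"; the SAP has the same assumption ("conservatively assuming an autocorrelation of .70"). The results follow: "we would have 80% power to detect a Cohen's d for the time by arm effect as small as 0.39" for Arms 2 and 3 together against TAU, and "as small as 0.55 for contrasts between individual arms".

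The analysis sections of both documents (Analysis of primary outcome) define the effect being powered. It is the coefficient of arm on the time slope in a two-level growth model with random intercept and slope. Outcomes are measured at baseline and months 2, 4 and 6 (Protocol section 4).

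Neither document says whether the 0.70 applies equally at all lags or decays with time. Neither gives its source, says why it is cautious, or defines the scale of d.

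**The concern.** Whether a correlation assumption is cautious depends on the estimand. For an arm difference averaged over time, a high correlation means that repeated measures add little, so assuming a high value is cautious. For a difference in change or slope, a high correlation removes between-person variance, so assuming a high value is favourable. The plan powers the second kind of effect but uses the adverb that suits the first.

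The structure matters as well. The word autocorrelation can be read as serial correlation that decays with lag, and baseline and month 6 are then far less correlated than 0.70.

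At stake is how the published detectable effects are read. A reader may take 0.55 and 0.39 as cautious figures and overrate what a null contrast says. The pilot is also meant to feed the power calculation of a full trial. The effect-size matrix described for that purpose varies d and does not mention the correlation, so the same assumption could be carried forward unexamined.

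**Working it through.** **Inputs from the documents.** Two-sided alpha 0.05, power 80%, correlation 0.70, and 81 retained. Allocation: "Participants will be randomized 1:1:1 to three conditions". With even loss this gives 27 per arm, so 27 vs 27 for a pairwise contrast and 54 vs 27 for the pooled one. There are four equally spaced visits, coded t = 0, 1, 2, 3.

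**Assumptions.** d is the slope-implied difference in change from baseline to month 6, divided by the cross-sectional SD (set to 1). There is no random-slope variance in the base case.

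**Formula.** d = K × sqrt(V × (1/n1 + 1/n2)). V is the variance of one person's slope-implied 6-month change, that is 3² × Var(slope). K = 1.960 + 0.842 = 2.802, or the t-based equivalent with n1 + n2 − 2 df.

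**Step 1: the plan's 0.55.** With equal correlation ρ, Var(slope) = (1 − ρ)/Σ(t − 1.5)² = (1 − ρ)/5. At ρ = 0.70, V = 9 × 0.30/5 = 0.54. Then d = 2.802 × sqrt(0.54 × 2/27) = 2.802 × 0.200 = 0.560, or 0.571 with t on 52 df. Power at 0.55 is 78.5% (normal) or 77.0% (t). The plan's figure is approximately reproduced.

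**Step 2: direction and structure.** For AR(1) 0.70 per visit the correlations at lags 1, 2 and 3 are 0.70, 0.49 and 0.343, and the GLS slope gives V = 1.313. Values below are t-based, with the normal approximation in brackets.

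| Correlation | V | Pairwise, 27 vs 27 | Pooled, 54 vs 27 |
|---|---|---|---|
| Equal 0.30 | 1.26 | 0.87 (0.86) | 0.75 (0.74) |
| Equal 0.50 | 0.90 | 0.74 (0.72) | 0.63 (0.63) |
| Equal 0.70 | 0.54 | 0.57 (0.56) | 0.49 (0.49) |
| Equal 0.80 | 0.36 | 0.47 (0.46) | 0.40 (0.40) |
| AR(1) 0.70 | 1.313 | 0.89 (0.87) | 0.77 (0.76) |

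The detectable effect falls as the correlation rises. AR(1) behaves the same way from about 0.3 upward (normal: 1.05 at 0.3, 1.01 at 0.5, 0.87 at 0.7, 0.56 at 0.9). Under AR(1) 0.70, pairwise power at 0.55 is about 41 to 42%, and about 69 per arm would be needed for 80%.

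For contrast, take the mean of all four visits, where V = (1 + 3ρ)/4. The pairwise figure then rises from 0.53 at ρ = 0.30 to 0.67 at ρ = 0.70. Only for that kind of effect is a high correlation the cautious choice.

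**Step 3: random slope.** The planned model includes one. Adding slope variance s per visit interval gives V = 0.54 + 9s at equal correlation 0.70. With assumed s of 0.02 and 0.05 SD², V = 0.72 and 0.99, and the pairwise d is 0.65 and 0.76 (normal).

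**Step 4: the pooled 0.39.** With the Step 1 inputs and 54 vs 27, d = 2.802 × sqrt(0.54 × (1/54 + 1/27)) = 2.802 × 0.173 = 0.485, or 0.491 with t on 79 df. Power at 0.39 is 61% (normal) or 60% (t).

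This mismatch does not depend on the correlation or on the scale of d, provided both contrasts use the same V. The ratio of pooled to pairwise must then be sqrt((1/54 + 1/27)/(2/27)) = sqrt(0.75) = 0.866, and 0.55 × 0.866 = 0.48. The published ratio is 0.39/0.55 = 0.71, which is 1/sqrt(2). That ratio would arise with 54 in each group, but TAU has 27.

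**The case against.** The strongest reply has four parts.

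- **The sponsor's calculation is not shown.** The reconstruction matches 0.55 but misses 0.39, so it cannot be claimed to be the SAS calculation. The figure 0.55 also arises in other ways. AR(1) 0.90 gives 0.56 to 0.57. A baseline-adjusted comparison at one follow-up with correlation 0.70 gives 0.545 to 0.555, and at month 2, which the SAP (Rationale and research questions) names as the primary time point, equal and serial correlation of 0.70 coincide. This stands, and 0.55 should not be called wrong. But the paragraph says it powers the time-by-arm effect in the HLM, and in a baseline-adjusted comparison too a higher correlation lowers the detectable effect.

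- **A reader might infer that 0.89 is the true figure.** The documents do not support that. It needs AR(1) per 2-month visit and the assumed scale of d. If serial decay is set so that baseline and month 6 correlate at 0.70, the normal approximation gives 0.59.

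- **A reader might infer that 0.55 is itself called conservative, or is close to a best case.** Neither holds. The adverb qualifies the 0.70, equal correlation 0.80 gives 0.47, and the documents contain no PHQ-9 correlation that would show the true value to be below 0.70.

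- **Nothing depends on the figure.** The funding cap sets the sample. Both documents repeat that the pilot is underpowered, and they treat its effect sizes as tentative. What a null contrast rules out is read from its confidence interval. This stands and limits the weight of the point. It does not justify the adverb or reconcile 0.39 with 0.55.

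**Conclusion.** The point holds in two limited parts.

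First, calling 0.70 conservative is unsupported for the effect the plan powers, because a higher correlation is the favourable direction. The pairwise 0.55 is approximately right under equal correlation 0.70 without random-slope variance. It is sensitive to that choice: 0.74 at equal 0.50, 0.47 at equal 0.80, 0.87 to 0.89 under AR(1) 0.70, and higher than the base case with a random slope. These values rest on the assumed scale of d and on 27 retained per arm. What is shown is the direction and the missing justification, not that the true correlation is lower than 0.70.

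Second, the pooled 0.39 is not delivered by the plan's own inputs. It should be about 0.49, with about 60% power at 0.39. This part is the firmer one, because 0.39 and 0.55 cannot both hold for 54 vs 27 and 27 vs 27 with a common variance.

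Practical weight is modest: no sample size, analysis or decision rule rests on either figure.

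**What to change.** In Protocol section 6.a and in the SAP, both under Power analysis, sample size:

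- Delete the adverb, or give the data or reasoning for expecting a correlation above 0.70.
- State the correlation structure, whether a random-slope variance was included, and the scale and time point of d.
- Restate the pooled detectable effect as about 0.49 for 54 vs 27 at equal correlation 0.70, or show the inputs that give 0.39.
- Report a sensitivity range on both sides of 0.70. For example, over equal correlation 0.50 to 0.80 plus AR(1) 0.70, the pairwise figure is about 0.47 to 0.89 and the pooled figure about 0.40 to 0.77. The sponsor should rerun this in its own program with the random slope included.

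The cost is a wording change in two documents, a short rerun, and less favourable published figures. Enrolment, follow-up, sample size and the analysis model stay as they are.

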Economic analysis. The future full trial will conduct a cost-effectiveness analysis (CEA) of the BLT intervention relative to TAU to inform the merits and costs of implementing such a program. In this pilot we will conduct both the relevant data collection and the economic analyses to prepare for this. Two major CEA cost components include 1) TAU costs related underlie all study arms, and 2) costs of the BLT intervention, including the equipment but also phone coach staff time. This pilot study provides the opportunity for our research team to hone the data collection process and measurement of these cost components, building on our several previous economic analyses conducted in concert with our mental health RCTs. While this pilot is underpowered to detect significant difference in costs between study conditions, we will be able to richly describe and categorize TAU services underlying each condition. In addition, [name] will lead efforts to estimate the total cost of the intervention by developing a data collection tool for phone coaches and research staff to track time used to the deliver the interventions. He will also periodically meet with those who are providing data to assess whether the tools are meeting their needs and if the data are truly capturing the resource intensity needed to deliver the protocol. This tool will be submitted in a subsequent modification.

Power analysis, sample size. The R34 pilot funding cap limits us to a feasibility sample that is insufficient for an adequately powered test of the hypothesis. Nonetheless, we provide an estimate of the statistical power obtained from this sample of a minimum of 90 participants (up to 100 pts if recruitment success

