## Hypotheses

While this is a pilot study and not powered to assess intervention effects, we hypothesize that the combined intervention (minimal + enhanced encouragement arms) will have larger reductions in PHQ-9 at post-acute treatment than the TAU control arm; and that enhanced encouragement will have larger reductions in PHQ-9 at post-acute treatment than minimal encouragement.

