## Management of missing data

Data can be missing for many reasons, including entry errors, interviewer omissions, treatment refusal, acute medical illness, etc. Missing data is also a consequence of attrition, but we expect dropout from the study will be less than 10% at the 6-month follow-up assessment. To carry out the planned ITT analyses, we use multiple imputation methodology to account for missing data[4, 5]. These methods preserve the correlational structure among the study measures and incorporates the uncertainty inherent in replacing missing values, and as with other imputation procedures, they assume data are “missing at random” (MAR). We will create 10 imputed datasets, repeating outcome analyses across each replicate, and will use Rubin’s rules to produce adjusted estimates and statistics from which inferences will be drawn[6].

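### The two detectable effects in the power paragraph, 0.39 for Arms 2+3 vs TAU and 0.55 for individual arms, cannot both be right under 1:1:1 allocation

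*Protocol*

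**What the plan says.** Protocol section 6, Data Analysis, under the power and sample size heading, sets out one scenario. The sample is fixed by "Assuming a retained sample size of $N=81$ at the final 6-month assessment", and the error rate and correlation by "At a two-tailed alpha level of 0.05 and conservatively assuming an autocorrelation of 0.70". At 80% power the detectable Cohen's d for the time-by-arm effect is then given as "0.39 for the contrast between active intervention arms (Arms 2 and 3) and TAU, and as small as 0.55 for contrasts" between individual arms. The SAP section on power and sample size repeats both figures for the same 81 retained.

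The group sizes are not printed, but they follow from the design. Protocol section 6, Randomization, states: "Participants will be randomized 1:1:1 to three conditions". The 81 is 90% of the 90 enrolled, in line with the SAP section on missing data: "we expect dropout from the study will be less than 10% at the 6-month follow-up assessment". Both documents also say that the funding-capped sample is "insufficient for an adequately powered test of the hypothesis".

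**The concern.** The two effects share one sample, one significance level, one power and one correlation. The only stated difference between the contrasts is how many participants are on each side. Pooling Arms 2 and 3 doubles one side and leaves TAU as it was, so precision should improve only modestly. The stated figures show the improvement expected if both sides had doubled.

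The pooled comparison is the first key contrast in SAP Aim 2, and it underlies the first SAP hypothesis, that the "combined intervention (minimal + enhanced encouragement arms) will have larger reductions in PHQ-9 at post-acute treatment than the TAU control arm". Both documents tell the reader that this contrast has 80% power at d = 0.39. If 0.55 is the correct figure of the pair, a true effect of 0.39 would be missed about 37% of the time rather than 20%. Because the pilot rehearses the methods of a larger trial, a group-size slip in the power calculation could also be carried forward.

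**Working it through.** **Inputs.** Two-sided alpha 0.05, power 80%, 81 retained, autocorrelation 0.70, detectable effects 0.39 and 0.55 (power paragraphs of both documents); 1:1:1 allocation (Protocol, Randomization). Assumption: equal retention, so 81/3 = 27 per arm, giving 54 vs 27 for the pooled contrast and 27 vs 27 for an individual contrast.

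**Formula.** Detectable d = (1.960 + 0.842) × √(f × (1/n1 + 1/n2)), where f is the variance factor from the repeated-measures model. The documents do not give f.

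**Reproducing the stated figures.** One simple choice is the baseline-adjusted factor f = 1 − 0.70² = 0.51.
- 27 vs 27: 0.545 (normal) or 0.555 (t), close to the stated 0.55.
- 54 vs 27: 0.472 (normal) or 0.477 (t), not 0.39.

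A four-visit slope with equal correlation of 0.70 gives 0.560 and 0.485. With first-order autoregressive correlation it gives 0.874 and 0.757. None of these gives both stated figures.

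**Ratio, which does not depend on f.**
- Required: √[(1/54 + 1/27) / (1/27 + 1/27)] = √0.75 = 0.866.
- Stated: 0.39/0.55 = 0.709.
- Rounding limits of the stated ratio: 0.385/0.555 = 0.694 to 0.395/0.545 = 0.725.

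**If 0.55 stands.**
- Back-solved f: (0.55/2.802)² / (2/27) = 0.520.
- Pooled detectable effect: 0.55 × 0.866 = 0.476 (t-based 0.473; 0.472 to 0.481 allowing for rounding of 0.55).
- Standard error at 54 vs 27: √(0.520 × 0.0556) = 0.170. Power at 0.39: Φ(0.39/0.170 − 1.960) = 63.1% (t-based 63.6%; 61% to 65% allowing for rounding of both figures).

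**If 0.39 stands.** The individual-arm figure is 0.39/0.866 = 0.450, and power at 0.55 would be 93%.

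**Could something else explain the pair?**
- *Uneven dropout.* Over all 55 splits of 81 with at most 30 per arm, and three individual contrasts each (165 ratios), the ratio runs from 0.809 to 0.982. With 0.55 as anchor, the pooled figure lies between 0.445 and 0.540.
- *More participants.* With 0.55 as anchor and no dropout, N = 90 gives 0.476 × √(81/90) = 0.452 and N = 100 gives 0.476 × √(81/100) = 0.429. Reaching 0.39 at 2:1 needs 81 × (0.476/0.39)², about 121 analysed, or 123 in whole arms of equal size.
- *Different significance levels.* A one-sided 5% test for the pooled contrast alone gives 0.42. A Bonferroni correction on the individual contrasts alone gives 0.43, 0.41 and 0.40 for division by 2, 3 and 4, and 0.39 only for division by 5. The text states a single two-sided 0.05.
- *Unequal variances between active arms and TAU.* The squared ratio becomes (v/2 + 1)/(v + 1), where v is the active-to-TAU variance ratio. Even at the rounding limit of 0.725, v would have to be about 19.

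**A possible source.** Doubling both groups multiplies the detectable effect by 1/√2 = 0.707, almost exactly the stated ratio. Anchored on 0.55, 54 vs 54 gives 0.55 × 0.707 = 0.389. That would need 108 participants, more than the maximum enrolment of 100. It looks as if 54 was used for each side, but the power code is not in the documents, so this is an inference.

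**The case against.** The absolute values depend on a SAS calculation and covariance structure that the documents do not show. The ratio therefore proves only that at least one figure is wrong, and both may be: under a four-visit slope with autoregressive correlation neither 0.39 nor 0.55 is recovered. Preferring 0.55 rests on a baseline-adjusted formula that is not the plan's growth model. This stands, and it is why both directions are given and the 0.48 and 63% are conditional on 0.55.

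The link to the SAP hypothesis is also loose. That hypothesis concerns PHQ-9 at 2 months, whereas the power figures are for the time-by-arm effect with 81 retained at 6 months. The Protocol's primary objective centres on Arm 3 against the other two arms and lists the pooled contrast under secondary objectives. This stands too: the 37% miss rate applies to the time-by-arm effect that the power paragraph describes, not to the 2-month endpoint.

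Finally, little depends on the number. The funding cap sets the sample size, both documents disclose the lack of power, and the planned sample-size matrix for the full trial is built around the observed pilot effect, not around 0.39. That limits the consequence, but it does not make the figure correct. Both documents chose to publish it. Whether 0.70 is a conservative correlation cannot be settled from the documents, and nothing here depends on it.

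**Conclusion.** The point holds. Under the stated design the two detectable effects are mutually inconsistent: their ratio should be 0.866 and is 0.709. At least one must be corrected. If 0.55 is right, the pooled effect detectable with 80% power is about 0.48, and power at 0.39 is 63% to 64%. If 0.39 is right, the individual-arm figure is about 0.45. The first reading is more likely, because a simple formula comes close to 0.55 at 27 vs 27, but this is not proven.

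The conclusion assumes that the two contrasts share one variance factor, one significance level and one power, as the text states. Equal retention is assumed for the central figures, but no retention pattern possible with 30 randomised per arm rescues the pair. This is a wrong descriptive figure that should be corrected, not a flaw in the design.

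**What to change.** Re-run the plan's own hierarchical-model power calculation with 54 vs 27 for Arms 2+3 against Arm 1 and 27 vs 27 for individual arms. Replace whichever figure, or both, the re-run does not support, in the power paragraphs of both the Protocol and the SAP. If 0.55 is confirmed, 0.39 becomes about 0.48. Add one clause giving the group sizes for each contrast and the covariance structure behind the autocorrelation, so that a reader can reproduce the result.

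The cost is one re-run of an existing calculation and a short text change in each document. If 0.55 is confirmed, the pooled figure becomes less favourable. Enrolment, conduct and the planned analyses stay as they are.

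### The protocol says a direct effect of 0.19 can be identified, but 0.19 matches the product of the two mediation paths and fits only the indirect effect

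*Protocol*

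**What the plan says.** The mediation power statement is in Protocol section 6.a, in the paragraph on power analysis and sample size. That paragraph first says the pilot is not powered for mediation and that these analyses will be run to try out the methods and obtain informative estimates. It then gives figures: "We estimate that we will have 80% power using a 95% bias-corrected confidence interval to identify effect sizes of 0.43 or larger" for the path from randomised arm to mediator and the path from mediator to outcome. After a semicolon it adds: "we will be able to identify direct and indirect effects of 0.19 or larger, which correspond to a small-medium effect".

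The paragraph does not name the scale of 0.43 or 0.19, or the N behind them. The only retained N it gives belongs to the growth-model calculation: "Assuming a retained sample size of $N=81$ at the final 6-month assessment". The paragraph on moderation and mediation in the same section calls the analysis exploratory. It estimates the indirect effect as a product of coefficients with a bias-corrected bootstrap. The SAP's power section has no mediation power statement.

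**The concern.** An indirect effect is the product of two coefficients. When both paths are individually detectable, their product can be small and still be detectable. A direct effect is one coefficient in the outcome regression, with its own standard error, and gains nothing from that. Applying one figure of 0.19 to both gives the direct effect a sensitivity that was worked out for something else.

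The 80% appears in the clause just before, and no other power level is offered, so a reader will naturally carry it across the semicolon. Anyone planning the full trial from this paragraph could then take 0.19 as a detectable direct effect at pilot size.

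**Working it through.** **Inputs**
- Two-sided alpha 0.05: "At a two-tailed alpha level of 0.05 and conservatively assuming an autocorrelation of 0.70". The 95% bootstrap interval corresponds to the same level.
- Paths a = b = 0.43; direct and indirect effect 0.19.
- Retained N=81. Allocation: "Participants will be randomized 1:1:1 to three conditions", so 27 per arm, 54 in a two-arm contrast, and 54 vs 27 when the active arms are pooled.
- Enrolled N=90: "the statistical power obtained from this sample of a minimum of 90 participants", with 100 as the maximum.
- Scale: standardised coefficients. This is an assumption.

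**Step 1. Where 0.19 comes from.** 0.43 × 0.43 = 0.185. A path reported as 0.43 may lie between 0.425 and 0.435, giving a product of 0.181 to 0.189. So 0.19 is consistent with multiplying unrounded paths, and the second decimal is not an error.

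**Step 2. Reproduce the plan's path and indirect figures.** Power for one coefficient r by Fisher z is Φ(√(N−3) × atanh(r) − 1.96), with atanh(0.43) = 0.460.
- N=54: Φ(7.141 × 0.460 − 1.96) = 0.907. Both paths significant: 0.907² = 0.82.
- N=81: Φ(8.832 × 0.460 − 1.96) = 0.982. Both paths: 0.982² = 0.96.

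Simulating the indirect effect with a 95% bias-corrected bootstrap (800 resamples, 1,500 to 3,000 replicates, no direct effect) gave 82% to 85% at N=54 and 96% to 97% at N=81. At N=81, 80% is already reached with both paths at about 0.34. The 80% is therefore met at N=54 and conservative at N=81.

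**Step 3. Same formula for a direct effect of 0.19**, with atanh(0.19) = 0.1923.

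| N | √(N−3) × 0.1923 | minus 1.96 | Power |
|---|---|---|---|
| 54 (two arms) | 1.374 | −0.586 | 28% |
| 81 (retained) | 1.699 | −0.261 | 40% |
| 90 (enrolled) | 1.794 | −0.166 | 43% |
| 100 (maximum) | 1.894 | −0.066 | 47% |

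Noncentral-t calculations, varying the overlap between arm and mediator and the variance the mediator explains, gave 34% to 48% at N=81 and 24% to 34% at N=54. The bias-corrected bootstrap of the direct effect gave 36% to 45% and 27% to 33%.

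**Step 4. Direct effect detectable with 80% power:** tanh(2.802 / √(N−3)).
- N=81: tanh(2.802 / 8.832) = 0.31.
- N=54: tanh(2.802 / 7.141) = 0.37.

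The N needed for 0.19 is (2.802 / 0.1923)² + 3, about 216.

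**The case against.** The strongest reply is that the paragraph disclaims mediation power before giving any figure, that the 80% is not repeated in the 0.19 clause, and that no decision depends on it. All of that is true and sets the weight of the point. It does not make the figure right, because the clause still offers 0.19 for the direct effect with no other power level attached.

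The second reply is that the scale is unstated. If 0.19 were Cohen's f², a single term would have ample power: 97% at N=81 and 88% at N=54 (noncentral F, noncentrality 0.19 × N). That reading fits the text poorly. The same 0.19 is given for the indirect effect, which the plan computes as a product of coefficients. An f² of 0.19 is also a partial correlation of √(0.19 / 1.19) = 0.40, close to the 0.43 paths, whereas the text calls 0.19 small to medium.

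The third reply is that adjusting for baseline PHQ-9 would help. Using the assumed 0.70 as the baseline correlation, residual variance falls to 1 − 0.49 = 0.51. Power becomes roughly Φ(0.19 × √(81 / 0.51) − 1.96) = 67% at N=81 and 50% at N=54, and more if the mediator explains further variance. But the protocol's worked example regresses follow-up PHQ-9 on the mediator and arm only, and the power sentence mentions no covariate.

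Three stronger readings are tempting, and the documents do not support them:
- *The mediation power statement as a whole is wrong.* On the standardised scale the path and indirect figures hold (step 2).
- *A null direct effect would be taken as full mediation.* The plan estimates the indirect effect only. It sets no test of the direct effect and no rule for full versus partial mediation.
- *The motivational-interviewing pathway must use N=54.* The momentary adherence questions go to Arms 2 and 3 only, but every participant is asked about BLT use and Arm 1 is to be described on similar metrics. N=54 there is an inference.

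**Conclusion.** The point holds for one word. As standardised coefficients in the regression the protocol describes, a direct effect of 0.19 has about 40% power at the retained N and 28% in a two-arm contrast. Even the maximum enrolment with no dropout stays below 50%. The path and indirect-effect figures stand.

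This rests on two assumptions: the standardised scale, which the documents do not name, and the use of N=81 (or 54) for mediation, which is borrowed from the growth-model calculation. With multiple imputation planned, N=90 is also arguable and gives 43%. The consequence is minor. The analysis is exploratory, it is stated to be unpowered, and neither the primary analysis nor the sample size depends on it.

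**What to change.** In the protocol's power paragraph, delete *direct* from the 0.19 statement. Alternatively, keep it and give the direct effect its own 80%-power detectable size: about 0.31 at N=81 and 0.37 at N=54, if the scale is standardised coefficients. In either case, name the scale of 0.43 and 0.19 and the N used, and say so if a baseline-adjusted model was assumed. The value 0.19 can stay for the indirect effect.

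The cost is a sentence of rewording. Design, sample size and analyses are unchanged, and the stated sensitivity for the direct effect becomes less favourable.
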